### 4. STUDY POPULATION

#### 4.1. Screening Data

Tables summarizing the disposition of patients will contain:

- The number of patients recruited;
- Number of patients with complete data from the two exams – % calculated from the total number of patients recruited;
- The number (%) of patients who withdrew from the study and the associated reasons (% calculated from the full set of analysis).

Unless otherwise specified, percentages will be calculated based on the number of patients in the full set of analysis.

#### 4.2. Eligibility

All patients with simultaneous recordings performed from the date of approval of the protocol until the proposed number of patients is completed. The following inclusion and exclusion criteria will be considered:

##### *Inclusion criteria*

Patients aged  $\geq 18$  years, with indication for continuous 24-hour electrocardiographic monitoring by 24-hour Holter at the IDPC outpatient clinic, and who agree to participate in the study by signing the free and informed consent form (ICF).

##### *Exclusion Criteria*

Refusal to provide consent for the study.

#### 4.3. Recruitment

All patients over 18 years of age who undergo Holter monitoring tests at the Electrophysiology and Cardiac Arrhythmias outpatient clinic of the Medical Section of Electrophysiology of the IDPC will be invited to participate in the study, and a prospective and consecutive recruitment of at least 182 patients with complete data from the two tests is expected.

#### 4.4. Study Discontinuation/Follow-up

N/A.

#### 4.5. Patient Baseline Characteristics

The baseline characteristics of the patients that will be analyzed descriptively will be the demographics and the underlying diseases. Frequency, percentage, and 95% CI, when appropriate, will be used to summarize the qualitative variables, and number of valid observations, mean, standard deviation (SD), median, interquartile range, and minimum and maximum values will be calculated for the quantitative variables.

## 5. ANALYSIS

### 5.1. Definition of Endpoints

#### *Primary Endpoint*

To compare the detection of arrhythmias between the two methods mentioned with regard to the set of the following arrhythmias: a) atrial fibrillation or atrial flutter; b) supraventricular tachycardia ( $\geq 3$  beats); c) ventricular tachycardia ( $\geq 3$  beats); d) polymorphic ventricular tachycardia or ventricular fibrillation; e) atrioventricular block (2nd degree Mobitz AVB I and II, 2:1 AVB and total AVB); and f) pauses ( $\geq 2.5$  seconds).

#### *Secondary Outcomes*

- Comparison of the detection of each type of arrhythmia between the two devices;
- Comparison of the duration of the examination between the two devices;
- Comparison of mean, minimum, and maximum heart rate captured between the two devices;
- Comparison of the total atrial ectopic heart beats captured between the two devices;
- Comparison of the total number of ventricular ectopic heart beats captured between the two devices;
- Comparison of total episodes of supraventricular tachycardia, ventricular tachycardia, and pauses between the two devices;
- Evaluate the convenience of using the two registration systems.

### 5.2. Methods of analysis

All measures resulting from each of the two techniques will be summarized using the descriptive measures cited in Section 4.5.

#### *Baseline characteristics*

The baseline characteristics mentioned in Section 4.5 will be presented in descriptive analysis tables. The percentages will be calculated according to the number of participants for whom the data is available. When there are missing values, the denominator will be described in the table and no assumptions or imputation will be made.

### Primary Endpoint

The comparison between the two methods in relation to the detection of arrhythmias will be evaluated by the accuracy of *QuoreOne* compared to Holter. The primary endpoint consists of the detection of any arrhythmia: a) atrial fibrillation or atrial flutter; b) supraventricular tachycardia ( $\geq 3$  beats); c) ventricular tachycardia ( $\geq 3$  beats); d) polymorphic ventricular tachycardia or ventricular fibrillation; e) atrioventricular block (2nd degree Mobitz AVB I and II, 2:1 AVB and total AVB); and f) pauses ( $\geq 2.5$  seconds). Other diagnostic statistics: Sensitivity, specificity, positive and negative predictive values will also be presented always followed by 95% confidence intervals.

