4.2. Primary Endpoint

To compare the detection of arrhythmias between the two methods mentioned with regard to the set of the following arrhythmias: a) atrial fibrillation or atrial flutter; b) supraventricular tachycardia (≥ 3 beats); c) ventricular tachycardia (≥ 3 beats); d) polymorphic ventricular tachycardia or ventricular fibrillation; e) atrioventricular block (2nd degree Mobitz AVB I and II, 2:1 AVB and total AVB); and f) pauses (≥ 2.5 seconds). The comparison between the two methods will be evaluated by the accuracy of *QuoreOne* compared to the conventional system, in addition to the other diagnostic statistics: sensitivity, specificity, positive and negative predictive values will also be presented always followed by 95% confidence intervals.

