## 2.3. Sample Size

The sample size calculation of the study was established assuming the hypothesis of comparability of the *QuoreOne* device in relation to the conventional device. According to data from a previous study, we have:

		Holter Any 6 (24 h)		Total
		No	At least 1	
Patch any 6 (24 h)	No	83	11	94
	Yes	2	50	52
Total		85	61	146

Any arrhythmias (of the 6 types atrioventricular block, pause, polymorphic ventricular tachycardia, supraventricular tachycardia, ventricular tachycardia, or atrial fibrillation)

From the data in the table above, we obtain the following proportions:

		Holter Any 6 (24 h)		Total
		No	At least 1	
Patch any 6 (24 h)	No	0.5685	0.0753	0.6438
	Yes	0.0137	0.3425	0.3562
Total		0,5822	0.4178	1.0000

Assuming that *QuoreOne* and Holter will agree to detect at least one arrhythmia event similar to that found between Patch and Holter in the reference study, a sample of 182 patients will have 80% power to show that the overall accuracy is greater than 85%, at a one-tailed significance level of 2.5%. (i.e., the lower limit of the 95% confidence interval (CI) should be above 85%). Therefore, this premise considers Holter as the "gold standard" test, and the accuracy of the *Quoreone* is evaluated in the detection of global arrhythmias (primary endpoint) and specific categories (secondary endpoints).

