### 3. STATISTICAL PRINCIPLES

#### 3.1. Confidence Intervals and p-Values

Two-tailed hypothesis tests with a significance level of 5% and confidence intervals of 95% will be used.

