### Secondary Outcomes

The individual categorical secondary endpoints (detection of each type of arrhythmia) will also be evaluated by diagnostic statistics (accuracy, sensitivity, specificity, positive and negative predictive values) with respective 95% confidence intervals.

The continuous secondary endpoints (mean, minimum and maximum heart rate, total atrial and ventricular ectopic heart beats, total episodes of supraventricular tachycardia, ventricular tachycardia and pauses) will be described by Bland-Altman plots accompanied by Lin and Pearson correlation coefficients.

Lists with the patients' reports will be made to evaluate the convenience of the systems. The Chi-square test or Fisher's exact test will be used to evaluate the proportion of patients who report greater comfort (comfort of the device) with *Quoreone* versus *Cardiolight*.

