### 5.4. Additional Analytics

The evaluation of agreement between the devices will also be performed from the Cohen Kappa statistic for the primary endpoint, and each of the secondary endpoints (arrhythmias criteria one by one).

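### The 85% accuracy criterion weights missed and extra detections equally, and no paired difference in detection rate is planned, so meeting it does not by itself support comparable detection

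*SAP*

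**What the plan says.** Protocol 1.3 sets out a hypothesis of comparability. Protocol 1.4.1 and SAP 1.2 make the primary objective whether QuoreOne's arrhythmia detection is comparable to Cardiolight's. Every patient wears both devices at once (SAP 2.2).

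For the primary endpoint (any of six arrhythmia types, yes or no per patient and device), SAP 5.2 states: "The comparison between the two methods in relation to the detection of arrhythmias will be evaluated by the accuracy of" QuoreOne compared with Holter. That section gives no limit. The limit appears only in SAP 2.3, where "the lower limit of the 95% confidence interval (CI) should be above 85"%. The design assumption there is that QuoreOne and "Holter will agree to detect at least one arrhythmia event similar to that found between Patch and Holter in the reference" study.

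Other planned outputs bear on the point:

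- **Composite:** "Sensitivity, specificity, positive and negative predictive values will also be presented always followed by 95% confidence intervals" (SAP 5.2). Protocol 4.2 has the same list: "in addition to the other diagnostic statistics: sensitivity, specificity, positive and negative predictive values will also be presented".
- **Each arrhythmia type:** "The individual categorical secondary endpoints (detection of each type of arrhythmia) will also be evaluated by diagnostic statistics" (SAP 5.2).
- **Agreement:** "The evaluation of agreement between the devices will also be performed from the Cohen Kappa statistic for the primary endpoint" and for each type (SAP 5.4).
- **Episode counts and other continuous measures:** Bland-Altman plots with Lin and Pearson coefficients (SAP 5.2).

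None of these has an acceptance limit or a stated part in the conclusion. Neither document names an interval or test for the difference between the two devices' detection rates.

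**The concern.** Accuracy is one minus the total disagreement rate. It cannot tell a device that misses Holter-detected arrhythmias from one that reports extra ones. Comparable detection is a claim about exactly that distinction. If the 85% criterion is met and most disagreements are misses, the plan does not say how the conclusion would be worded. A report could then claim comparable detection on the strength of accuracy although the same data show that QuoreOne detects significantly fewer patients with arrhythmia.

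**Working it through.** **Inputs.** The planning table in SAP 2.3 (n = 146): both negative 83; Holter only (missed by the patch) 11; patch only (extra) 2; both positive 50. Criterion: lower 95% limit above 85%. N = 182, power 80%, one-sided 2.5%.

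**1. The plan's own figure.** Assumed accuracy = (83 + 50)/146 = 133/146 = 0.911. With a Wald limit at n = 182, at least 163 agreements are needed: 163/182 = 0.8956, and 0.8956 - 1.96 × √(0.8956 × 0.1044/182) = 0.851. With 162 agreements the limit falls to 0.845. The exact binomial probability of 163 or more at 0.911 is 80.7%, so 182 is reproduced. With an exact (Clopper-Pearson) limit, 165 agreements are needed and the probability is 64.4%. The SAP does not name the interval method, so both are carried below.

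**2. The planning table against the criterion.**

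- Accuracy 91.1%; lower limit 86.5% (Wald) or 85.3% (exact). The criterion is met.
- Sensitivity 50/61 = 82.0% (exact 95% CI 70.0 to 90.6). Specificity 83/85 = 97.6%.
- Paired difference in detection rate = (extra - missed)/n = (2 - 11)/146 = -6.2 points; Tango score 95% CI -11.8 to -1.6.
- Uncorrected McNemar z = (2 - 11)/√13 = -2.50, p = 0.013; exact McNemar p = 0.022.

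**3. Same accuracy, different direction.** Hold the 13 disagreements, 61 Holter-positives and 85 Holter-negatives fixed:

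| Missed / extra | Accuracy | Sensitivity | Paired difference, points (Tango 95% CI) | Kappa |
|---|---|---|---|---|
| 11 / 2 | 91.1% | 82.0% | -6.2 (-11.8 to -1.6) | 0.813 |
| 7 / 6 | 91.1% | 88.5% | -0.7 (-6.1 to 4.6) | 0.817 |
| 2 / 11 | 91.1% | 96.7% | +6.2 (1.6 to 11.8) | 0.821 |

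Accuracy does not move and kappa hardly does. Sensitivity and the paired difference do.

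**4. The extreme case at n = 182.** At the planning rate there are 182 × 0.4178 ≈ 76 Holter-positives. The rule tolerates 19 errors (Wald) or 17 (exact). If all are misses, sensitivity is 57/76 = 75.0% or 59/76 = 77.6%, and the criterion is still met.

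**5. How often this could happen.** Enumerate all outcomes at n = 182 with total disagreement 13/146 and vary only the true missed:extra split. The chance of meeting the criterion is 80.7% (Wald) or 64.4% (exact) for every split. Among trials that meet it, the share with significant under-detection (uncorrected McNemar, two-sided 5%) is:

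| True split | Wald limit | Exact limit |
|---|---|---|
| 11:2 | 81% | 79% |
| 10:3 | 56% | 54% |
| 9:4 | 31% | 30% |
| 7:6 | 4.6% | 4.5% |
| even | 2.4% | 2.4% |

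With the exact McNemar test the 11:2 figures become 74% and 71%.

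**The case against.** The plan does not present accuracy alone. Sensitivity and specificity with confidence intervals stand beside it, and in the planning table 82.0% against 97.6% shows the imbalance at once. SAP 5.2 also has each technique's measures summarised descriptively, which can be read to cover each device's detection rate. With Holter declared the reference in SAP 2.3, sensitivity and specificity are the usual directional measures, and the paired difference follows arithmetically from the same 2×2 table. The paired difference can even conceal errors. With 8 missed and 8 extra among 182 patients, and 76 Holter-positives assumed, it is 0 (Tango -4.7 to 4.7 points) while sensitivity is 68/76 = 89.5%.

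Most of this stands, and it limits the point. A reader might infer that no paired comparison is planned at all. The documents do not support that: kappa and the Bland-Altman plots are within-patient comparisons, and the diagnostic statistics come from the paired table. A reader might also object that two devices could report different arrhythmia types and still count as agreeing on the composite. The per-type statistics and per-type kappa largely cover this, and the documents give no mismatch rate from which to size it.

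What the objection does not answer is narrower. No interval or test for the difference in detection rate is planned for the binary primary endpoint. Separate descriptive percentages for each device do not supply one. And nothing ties the directional results to the conclusion.

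**Conclusion.** The concern holds in this limited form. Meeting the only numerical criterion shows overall agreement with Holter above 85%; it does not by itself show comparable detection. The SAP's own design assumption would meet the criterion with a statistically significant deficit of 6.2 points in detection.

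A reader might take that, or the 81% figure, as a forecast that QuoreOne will under-detect. The documents do not support this. The table describes another patch, the split of errors for QuoreOne is unknown, and the share runs from about 2% to about 80% over the splits considered (71% to 74% at 11:2 with the exact test). These figures assume the planning table's total disagreement of 13/146; the sensitivities in the extreme case also assume its 41.8% Holter-positive rate.

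This should be changed, but it does not invalidate the design. The directional data will be collected and reported; what is missing is a direct paired estimate and a rule for wording the conclusion.

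**What to change.** Leave accuracy, the 85% criterion and the 182 patients as they are, and add no further pass/fail condition: the documents give no basis for a margin. In SAP 5.2, under the primary endpoint:

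1. Add as supportive output the paired difference in detection rate (QuoreOne minus Holter) with a Tango score 95% CI and the uncorrected McNemar test. Use the two-sided 5% level of SAP 3.1 ("Two-tailed hypothesis tests with a significance level of 5% and confidence intervals of 95% will be used"). This McNemar test is the Tango score statistic at zero difference, so interval and test cannot contradict each other.
2. State that meeting the criterion supports the conclusion *overall agreement with Holter above 85%*.
3. State that any claim of comparable detection is reported with sensitivity (95% CI) and the paired difference, that significant under-detection is stated as such, and that a non-significant difference is not read as equivalence. Sensitivity has to stay alongside because balanced errors cancel in the difference.

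This is a cheap improvement: some SAP wording and one extra table from data already collected. The sample size, the primary statistic and the chance of meeting the 85% criterion do not change. The downside is that the conclusion may have to be worded less favourably.

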### Secondary Outcomes

The individual categorical secondary endpoints (detection of each type of arrhythmia) will also be evaluated by diagnostic statistics (accuracy, sensitivity, specificity, positive and negative predictive values) with respective 95% confidence intervals.

The continuous secondary endpoints (mean, minimum and maximum heart rate, total atrial and ventricular ectopic heart beats, total episodes of supraventricular tachycardia, ventricular tachycardia and pauses) will be described by Bland-Altman plots accompanied by Lin and Pearson correlation coefficients.

Lists with the patients' reports will be made to evaluate the convenience of the systems. The Chi-square test or Fisher's exact test will be used to evaluate the proportion of patients who report greater comfort (comfort of the device) with *Quoreone* versus *Cardiolight*.

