2.5. Data Collection

All exams will be performed at IDPC, the exams performed with the Cardiolight equipment will be stored both in the original file (.xcm) and in the final version of the report (.pdf). The exams performed with the QuoreOne equipment will be saved directly on the online report platform and in the final version of the report (.pdf). These files will be exported to an external hard drive and sent for tabbing. If there has been a report of symptoms by the patient, this data will be included in both files to establish the relationship between the complaint and any alteration in the electrocardiogram. The parameters will be analyzed with anonymized data from the participants.

After the Holter devices are removed, the participant will be asked to answer a questionnaire about the convenience of use and functions of the *QuoreOne* device.

3. Methodology

The exams performed by the conventional system (*Cardiolight*, Cardios) and by the *QuoreOne* system will be analyzed and the reports released by physicians from the Electrophysiology Section of the IDPC. These tests will be implemented at the same time in the same patient and for the same duration. The physicians evaluating the results of one method will be the same as the physicians evaluating the results obtained by the other method, but these will be blinded to the patients' data, making it impossible to identify that the tests being evaluated are from the same patient.

4. Statistical analysis

4.1.Descriptive Analysis

Data will be collected regarding demographic variables, underlying diseases, use of medications, and medical indication for Holter monitoring. Categorical variables will be presented with counts and percentages. Quantitative variables will be presented as means and standard deviations if normal distribution and as medians and interquartile ranges if non-Gaussian distribution. The Kolmogorov-Smirnov test will be used to evaluate the normality of the distributions of quantitative variables.

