4.3. Secondary Endpoints

Comparison of the detection of each type of arrhythmia between the two devices

- Comparison of the duration of the examination between the two devices;
- Comparison of mean, minimum, and maximum heart rate captured between the two devices;
- Comparison of the total atrial ectopic heart beats captured between the two devices;
- Comparison of total ventricular ectopic heart beats captured between the two devices;
- Comparison of total episodes of supraventricular tachycardia, ventricular tachycardia, and pauses between the two devices;
- Evaluate the convenience of using the two registration systems.

The individual categorical secondary endpoints (detection of each type of arrhythmia) will also be evaluated by diagnostic statistics (accuracy, sensitivity, specificity, positive and negative predictive values) with respective 95% confidence intervals.

The continuous secondary endpoints (mean, minimum and maximum heart rate, total atrial and ventricular ectopic heart beats, total episodes of supraventricular tachycardia, ventricular tachycardia and pauses) will be described by Bland-Altman plots accompanied by Lin and Pearson correlation coefficients.

Lists with the patient's reports will be made to evaluate the convenience of the systems. The Chi-square test or Fisher's exact test will be used to evaluate the

proportion of patients who report greater comfort (comfort of the device) with *Quoreone* versus *Cardiolight*.

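### No ratio-scale or count-band analysis is named for total ectopic beats; if counts are strongly skewed (log-SD about 2 or more), the planned agreement output can miss two-way miscounting confined to lower-count patients

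*SAP*

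**What the plan says.** The comparison of ectopic totals is a listed secondary outcome (SAP 5.1: "Comparison of the total atrial ectopic heart beats captured between the two devices", with a matching item for ventricular beats). The method is one sentence in SAP 5.2, Secondary Outcomes, which covers mean, minimum and maximum heart rate together with "total atrial and ventricular ectopic heart beats, total episodes of supraventricular tachycardia, ventricular tachycardia and pauses) will be described by Bland-Altman plots". Protocol 4.3 says the same: these endpoints "will be described by Bland-Altman plots accompanied by Lin and Pearson correlation coefficients". Neither place states a scale, a transformation or a split by count level, and no agreement threshold in beats is set.

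Three other provisions come near but do not fill the gap:

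- Protocol 4.1 presents quantitative variables "as medians and interquartile ranges if non-Gaussian distribution". That governs description, not the agreement analysis.
- SAP 5.2 opens with "All measures resulting from each of the two techniques will be summarized using the descriptive measures cited in Section 4.5", and SAP 4.5 lists "number of valid observations, mean, standard deviation (SD), median, interquartile range, and minimum and maximum values". These summarise each device separately and are not paired.
- SAP 5.4 adds Cohen's kappa for the primary endpoint and "each of the secondary endpoints (arrhythmias criteria one by one". Kappa and the diagnostic statistics concern presence of the six arrhythmia types. Ectopic beats are not among them.

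**The concern.** Limits of agreement in beats assume that one spread of differences describes every patient. Counting error usually grows with the count, and any adult with a Holter indication is eligible, with no restriction on ectopic burden. If counts range from a handful to thousands, the spread is set by the few highest counts. The limits are then too wide for the typical patient and too narrow for the high-burden one.

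Lin's coefficient has the same weakness, because it is a ratio of squared beats: 1 − Lin = (s_d² + d̄²)/(s_x² + s_y² + d̄²), where d is the paired difference. As an example, a 10% error on 2,000 beats adds 200² = 40,000 to the sum of squares. A 50% error on 20 beats adds 10² = 100. One such patient outweighs 400 of the other kind, in a trial of 182.

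Two things are at stake. A device that miscounts most low- and mid-count patients in either direction may look much like a good one. And a good device may look poor, because its limits exceed most patients' counts.

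**Working it through.** **The plan's own figures.** The documents state no figure for the ectopic-count analysis. The sample size is used below, so it was checked first. With expected accuracy (83 + 50)/146 = 0.911, the rule that a Wald 95% lower limit exceeds 85% needs at least 163 of 182 correct, and its power is 80.7%, in line with the stated 80%.

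**Inputs.** From the documents: n = 182 and the named analysis. Assumed, because the documents are silent:

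- Cardiolight count: Poisson with a log-normal rate, median 20, log-SD s = 1.5, 2.0 or 2.5, capped at 40,000.
- Good device: log error SD 0.10 (about 10%) in every patient.
- Miscounting device: the same error in the 18 highest counts. In the rest, a random half lose 50% and the other half gain 50%.

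Limits are d̄ ± 1.96·s_d. Ratio limits are the same calculation on log(count + 1), back-transformed. Figures are means over 1,000 simulated trials.

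| | s = 1.5 | s = 2.0 | s = 2.5 |
|---|---|---|---|
| Lin, good | 0.994 | 0.995 | 0.995 |
| Lin, miscounting | 0.980 | 0.990 | 0.994 |
| Half-width in beats, good (5th–95th percentile of trials) | 30 (14–67) | 111 (32–257) | 330 (80–904) |
| Half-width in beats, miscounting | 52 (36–80) | 135 (62–313) | 356 (112–874) |
| Mean difference, miscounting | 0.2 | 0.5 | 1.4 |
| Patients off by at least a quarter of their count, miscounting | 82% | 78% | 74% |
| Ratio limits, good | 0.84–1.20 | 0.84–1.19 | 0.85–1.18 |
| Ratio limits, miscounting | 0.33–2.42 | 0.34–2.37 | 0.35–2.32 |
| Count band 10–99, 2.5th to 97.5th percentile, good | −8 to 9 | −8 to 9 | −8 to 10 |
| Same, miscounting | −40 to 40 | −41 to 41 | −41 to 42 |

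At s = 2 and above, the raw half-widths of the two devices overlap almost wholly from trial to trial. The ratio limits and the count band separate them clearly. Repeating the simulation gave half-widths of 106 v 128 (s = 2) and 304 v 330 (s = 2.5), and Lin 0.994 v 0.991 and 0.995 v 0.993.

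**Limits against the patient's own count.** For the good device with 10% error, the half-width exceeds the patient's count in 57%, 75% and 83% of patients. A hand check is Φ(ln(h/20)/s):

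- s = 1.5: Φ(ln 1.5/1.5) = Φ(0.27) = 61%
- s = 2.0: Φ(ln 5.55/2) = Φ(0.86) = 80%
- s = 2.5: Φ(ln 16.5/2.5) = Φ(1.12) = 87%

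These are slightly above the simulated values because the half-width varies between trials. The same limits cover only 65%, 71% and 75% of the top-decile patients, against a nominal 95%. On the raw plot 74%, 87% and 92% of points lie in the leftmost 5% of the axis.

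**Sensitivity to device error.** With 3% to 10% error the share is about 52% to 83% at s = 2 to 2.5. At s = 1.5 it is only 28% (3% error), about 40% (5%) and 57% (10%).

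**Other assumptions.** Take median 50, 5% error and an added ±80% below the median. At s = 2 the half-width moves from 89 to 95 and Lin stays at 0.999, while the 95% ratio factor goes from 1.10 to 3.7. At s = 0.5 the raw output does react: half-width 6 to 40, Lin 0.99 to 0.81.

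**Where the planned output works** (median 20):

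- s = 1.0, the two devices above: Lin 0.94 v 0.99, half-width 28 v 10.
- A random 90% of patients halved: Lin 0.80 to 0.82. A random 90% off by ±50%: Lin 0.87 to 0.88.
- Lowest 90% all halved: mean difference −13 to −27 beats, its interval excluding zero in every trial; medians 20 v 10.

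**The case against.** The strongest reply is that the text does not fix the scale. A Bland-Altman plot may be drawn on a log or ratio axis, and for descriptive endpoints with no acceptance limit an analyst could choose it on seeing the scatter. That stands as far as it goes: a reader might infer that the plan commits to raw beats, and it does not say so. Raw differences are still the standard reading of the sentence, and an unnamed scale is chosen after the data are seen.

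The second reply is that the harm needs several assumptions together: strong skew, two-way error near 50%, confinement to the lower counts, and near-balance of gains and losses. This is correct. Nothing in the documents suggests that either device errs this way, and the planned output works when one of these conditions fails.

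Third, the per-device quartiles give hints. At log-SD 1.5 the first quartile moves from about 7 to 6 and the median from 20 to 17; at log-SD 2 the first quartile moves from 5.2 to 4.2. These are real but unpaired, and cannot show how many patients are miscounted.

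A reader might also infer that the limits exceed most patients' counts from log-SD 1.5 upward. That depends on device error and fails at 3% to 5%. Nor does the plan present Pearson as evidence of agreement: it reports Lin beside it.

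**Conclusion.** The point holds as an optional improvement. The omission is plain in both documents. Its consequence is conditional on strong right skew, log-SD about 2 or more, which is an assumption. Under it, one pair of limits exceeds the patient's own count in about 52% to 83% of patients, is too narrow for high counts, and Lin stays near 1 despite two-way errors of about 50% in most lower-count patients. At log-SD 1.5 the effect is partial: Lin 0.98 v 0.99 and half-widths of about 52 v 31 beats give some signal. At 1.0 the raw output separates the devices.

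It would be wrong to conclude that serious miscounting in general goes unseen. One-way loss, and error that reaches the high counts, both show. It would also be wrong to carry this over to the main result: the endpoints are secondary and descriptive, and the primary conclusion and n = 182 are unaffected.

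**What to change.** In SAP 5.2 and Protocol 4.3, for total atrial and total ventricular ectopic beats, add:

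1. a Bland-Altman analysis on log(count + 1), back-transformed to a mean ratio with 95% limits;
2. paired differences by bands of Cardiolight count fixed before analysis (for example 0, 1–9, 10–99, 100–999, 1,000 or more), with the median and the 2.5th and 97.5th percentiles, or the range in small bands.

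Keep the raw plot and raw Lin. They catch high-burden loss that the log scale misses: with the nine highest counts halved, raw Lin is 0.80 to 0.81 but Lin on the log scale is 0.994 to 0.997. Heart rates need no change.

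Optionally use the same display for supraventricular tachycardia, ventricular tachycardia and pause totals, since kappa and the diagnostic statistics assess presence, not number. Give those ratio limits only in patients with at least one episode on either device, because zero pairs narrow them. In the SAP 2.3 planning table ("Any arrhythmias (of the 6 types atrioventricular block, pause, polymorphic ventricular tachycardia, supraventricular tachycardia, ventricular tachycardia, or atrial fibrillation"), 83 of 146 patients (0.5685) are negative on both devices, which scales to 0.5685 × 182 = 103.5. A reader might take about 103 as the expected number of zero pairs for each episode type. It is only a floor, because the table counts patients negative for all six types, and it comes from a different patch device.

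The cost is some wording, plus one extra plot and one extra table per total, from data already collected. The ratio limits depend somewhat on the offset at low counts: 0.33 to 2.41 with +1 becomes 0.30 to 2.58 with +0.5. The count bands make that visible.
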